4.5. MODIFIED FATIGUE IMPACT SCALE (MFIS)

The MFIS is a detailed tool that is completed by the subject. Scoring is simple, the score reflects functional limitation due to fatigue experienced within the previous 7 days rather than a measure of the current level of fatigue.

In REN001-201 subjects will perform the MFIS at Screening, Baseline, Week 4 (Month 1), Week 12 (Month 3), Week 18 (Month 4.5) and Week 24 (Month 6). In REN001-202 subjects will be assessed at Baseline, Months 1, 3, 6, 12, 18 and 24; which from the start of REN001-201 are equivalent to Months 6, 7, 9, 12, 18, 24 and 30. It will also be assessed at an early termination visit if the subject withdraws from the study.

There are 21 items, each of which is scored 0 (never) to 4 (almost always), providing a continuous scale of 0–84. It is composed of three subscales that describe the impact of fatigue on physical (9 items), cognitive (10 items) and psychosocial functioning (2 items). Physical functioning reflects motivation, effort, stamina and coordination. Cognitive functioning concerns concentration, memory, thinking and organization of thoughts. Psychosocial functioning describes the impact of fatigue upon isolation, emotions, workload and coping. All items are scaled so that a higher score indicates a greater impact of fatigue. The below table shows how to calculate the 3 subscales and the total score:

Subscale	Items	Range
Physical	4+6+7+10+13+14+17+20+21	0 – 36
Cognitive	1+2+3+5+11+12+15+16+18+19	0 – 40

Subscale	Items	Range
Psychosocial	8+9	0 – 8
Total Score	Physical + cognitive + psychosocial subscales	0 – 84

There is no recommended methodology for handling missing component scores for this questionnaire, however, to utilize all available data the following is proposed:

- if 50% or more of the component scores are missing, then the subscale will not be derived and as a result the total score will not be derived. In this situation the subscale(s) with $\geq 50\%$ missing component scores and the total score will be considered missing
- if less than 50% of the component scores are missing then the average, rounded up to the nearest integer, of the non-missing scores for the subscale will be used to impute each missing value

For each visit changes from baseline and percent changes from baseline will be calculated for each of the sub-scale scores and the total score.

4.6. 36 ITEM SHORT FORM SURVEY (SF-36)

The SF-36 version 2.0 Health Survey asks questions, with a one week recall period, which cover 8 health concepts: physical functioning, bodily pain, role limitations due to physical health problems, role limitations due to personal or emotional problems, mental health, social functioning, vitality (referred to in the protocol as energy/fatigue) and general health perceptions. It also includes a single item that provides an indication of perceived change in health. If REN001 is effective greater improvements are anticipated with vitality than the other health concepts.

In REN001-201 the SF-36 will be used at Baseline, Week 4 (Month 1), Week 12 (Month 3), Week 18 (Month 4.5) and Week 24 (Month 6). In REN001-202 subjects will be assessed at Baseline, Months 1, 3, 6, 12, 18 and 24; which from the start of REN001-201 are equivalent to Months 6, 7, 9, 12, 18, 24 and 30. It will also be assessed at an early termination visit if the subject withdraws from the study.

All scale scores will be derived using QualityMetric Health Outcomes Scoring Software 5.0. This software generates standardized scores in accordance with the standards set by the developers of the survey. All items are scored so that a high score defines a more favourable health state. In addition, each item is scored on a 0 to 100 range.

For each visit changes from baseline will be calculated for each health concept scale.

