10.2. MODIFIED FATIGUE IMPACT SCALE (MFIS)

Observed, change from baseline and percent change from baseline values will be summarized by visit using descriptive statistics, for the subscale scores and total score. The associated 95% confidence intervals for the observed, change from baseline and percent change from baseline means will also be presented. The number of subjects withdrawn prior to the visit or with missing data will also be presented.

Mean plots of observed, change from baseline and percent change from baseline values, with 95% confidence intervals will be presented by group with visit on the x-axis. A reference line for no change (i.e., $y=0$) will be included in the change from baseline plot.

Spaghetti plots for the changes from baseline will be plotted over time. The plots will be split by group. The y-axis will be uniform across the plots to allow comparisons. A reference line for no change (i.e., $y=0$) will be included.

Categorical shift tables of change from baseline showing improvement (at least a 4-point decrease in score), no change (less than a 4-point change in either direction) or worsening (at least a 4-point increase in score) at each visit will be summarized. The table will include categories for withdrawn and missing. Percentages will not be presented for the withdrawn and missing rows, and the percentages presented will use the number of non-

missing values as the denominator. In addition, to account for subjects at the extreme ends of the scale, the shift table will also include the percent improving or worsening based on those subjects who have the potential to improve or worsen respectively.

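### Filling missing MFIS items with a rounded-up subscale mean inflates partly completed fatigue scores by about 0.4 points per imputed item on average

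*SAP*

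**What the plan says.** SAP 4.5 describes the MFIS as 21 items scored 0 to 4, in physical (9 items), cognitive (10) and psychosocial (2) subscales. On direction it states: "All items are scaled so that a higher score indicates a greater impact of fatigue".

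For missing items it observes that "There is no recommended methodology for handling missing component scores for this questionnaire" and then sets its own rule, with the aim of using all available data. If half or more of a subscale's items are missing, that subscale and the total are left missing. If fewer than half are missing, "the average, rounded up to the nearest integer, of the non-missing scores for the subscale will be used to impute each missing value". No reason is given for rounding up. Protocol 7.3.1 gives the summation formulae but no missing-item rule.

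SAP 10.2 summarises observed values, change and percent change with 95% confidence intervals. It also tabulates shifts at a fixed threshold, with improvement defined as "at least a 4-point decrease in score" and worsening as the mirror image.

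SAP 8.3.1 says missing efficacy data will not be imputed, and the opening of SAP 10 refers to complete-case handling. Neither mentions the MFIS item rule.

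**The concern.** Replacing a missing item with the subject's own subscale mean adds no systematic error if the missing items resemble the answered ones. Rounding that mean up breaks this, because the error can only go one way. The same rounded value fills every gap in the subscale, so the excess is multiplied by the number of items missing.

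The rule applies at baseline as well as follow-up, so it cannot be defended as conservative. An inflated baseline makes a subject appear to improve; an inflated follow-up makes the subject appear to worsen. At stake are the MFIS means and shift tables, a secondary endpoint for mtDNA-PMM subjects and an exploratory one for nDNA-PMM subjects.

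**Working it through.** **Inputs from SAP 4.5 and 10.2.** Items are integers 0–4; subscales have 9, 10 and 2 items; imputation applies only below 50% missing; the shift threshold is 4 points. The stated ranges reproduce: 9 × 4 = 36, 10 × 4 = 40, 2 × 4 = 8, total 84.

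**Which subscales are imputed.** Physical: up to 4 of 9 missing (44%). Cognitive: up to 4 of 10 (40%). Psychosocial: never, since 1 of 2 is already 50%.

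**Excess over the unrounded mean.** With k items missing, m observed and observed sum S, the excess is k × (ceil(S/m) − S/m). It is zero when S/m is an integer and otherwise positive. The largest fractional gap is (m − 1)/m, so the maximum excess is k(m − 1)/m. This needs no assumption.

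The average excess needs an item distribution, which the documents do not give. The table shows the range over four assumed distributions (uniform, and weighted to low, middle or high scores), calculated exactly.

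| Subscale | Missing | Average excess | Maximum excess |
|---|---|---|---|
| Physical | 1 of 9 | 0.420–0.439 | 1 × 7/8 = 0.875 |
| Physical | 2 of 9 | 0.826–0.864 | 2 × 6/7 = 1.71 |
| Physical | 4 of 9 | 1.562–1.613 | 4 × 4/5 = 3.20 |
| Cognitive | 1 of 10 | 0.425–0.444 | 1 × 8/9 = 0.889 |
| Cognitive | 2 of 10 | 0.840–0.878 | 2 × 7/8 = 1.75 |
| Cognitive | 4 of 10 | 1.616–1.684 | 4 × 5/6 = 3.33 |

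Per imputed item the average is 0.39 to 0.44. The observed mean was an integer, so that nothing was added, in about 11–22% of cases. The largest possible excess on the total is 3.20 + 3.33 = 6.53.

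**Against the true missing items.** In a simulation with correlated items (assumed latent correlation 0.5, items missing at random), the bias with rounding up was 0.415–0.463 points for one missing item and 1.506–1.707 for four. With the unrounded mean it was −0.003 to +0.006.

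**Crossing the threshold with one item missing.** Take a complete baseline physical score of 16. At follow-up eight items are answered with sum 17, so the mean is 17/8 = 2.125.

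- SAP rule: impute 3, score 17 + 3 = 20, change +4, worsening.
- Unrounded mean: score 17 + 2.125 = 19.125, change +3.125, no change.
- Conventional rounding: score 17 + 2 = 19, change +3, no change.

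Swap the visits and the SAP rule gives −4, improvement, where the other two give no change. SAP 10.2 does not say whether the shift table covers subscales, total or both; if the other subscales are complete and unchanged, the total moves identically.

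**Effect on a group mean.** If a share p of forms at one visit lacks one item, the mean shifts by about p × 0.44. That is 0.004 points at an assumed 1%, 0.022 at 5% and 0.088 at 20%, on a 0–84 scale.

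**The case against.** The strongest reply is that this hardly matters. No testing is planned (SAP 8.1), SAP 2 asks that efficacy be read descriptively, and only partly completed forms are touched. That stands.

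On the shift tables, simulated misclassification of the total with one item missing at follow-up was 4.2% under both the SAP rule and the unrounded mean. With two items missing in one subscale it was 7.5% against 6.0%. Only with four missing in both the physical and cognitive subscales was the gap wide (22% against 13%). So with one missing item the fix does not reduce the number of misclassified subjects. What it removes is the lean: errors under rounding up fall mostly on one side, while those under the unrounded mean roughly balance.

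The phrase may also be a loose description of conventional rounding, which gives only about −0.01 to +0.09 points per item in the exact calculation. That is possible, but a programmer following the text would code a ceiling.

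A reader might infer more than the documents support:

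- That every imputed score is inflated. Integer means are unchanged and the psychosocial subscale is never imputed.
- That errors of 3 points are typical. An average of 3.2 to 3.3 points on the total (1.562 + 1.616 up to 1.613 + 1.684) needs 8 of 21 items missing, the most the rule allows.
- That the rule favours or disfavours the drug. The direction depends on which visit has the gaps, and with equal missingness it cancels on average, though not subject by subject.

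**Conclusion.** The point holds in a limited form. The rule as written never rounds down, and on average it inflates partly completed physical and cognitive scores by about 0.4 points per imputed item. The direction and the maxima (3.20 and 3.33 points) follow from SAP 4.5 alone. The average rests on assumed item distributions, and the near-zero bias of the unrounded mean assumes that missing items resemble answered ones.

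The overall effect cannot be sized because no item-missing rate is given; it is probably small. It is still worth correcting: the bias is systematic and unexplained, and integers are not needed, since SAP 4.7 already scores BPI severity as a plain mean of the non-missing items.

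**What to change.** In SAP 4.5, delete the rounding phrase and impute with the unrounded mean of the non-missing items in that subscale, keeping the 50% rule. Apply this identically to REN001-201 and REN001-202 MFIS data in this report. SAP 3.8 combines the two studies and uses the REN001-201 Week 24 visit as baseline for most mtDNA-PMM subjects, so mixed scoring would itself distort change. In SAP 8.3.1, name the MFIS item-level rule as an exception to the no-imputation statement, and align the complete-case reference in SAP 10.

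The cost is a few words, some non-integer scores, and a check against REN001-201. That study's SAP is not among these documents; if it rounds up, some scores will differ slightly from its CSR, and a note should say so. SAP 2 allows amendment until database lock.

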7.3 Quality of Life PROs

7.3.1 Modified Fatigue Impact Scale (MFIS)

The MFIS is a 21-item scale, the score reflects functional limitation due to fatigue experienced within the previous 7 days rather than a measure of the level of fatigue. It may be used in both the clinical and the research setting in people for whom fatigue is a predominant symptom.

There are 21 items, each of which is scored 0 (never) to 4 (almost always), providing a continuous scale of 0–84. It is composed of three subscales that describe the impact of fatigue on physical, cognitive and psychosocial functioning:

Physical functioning (9 items) reflects motivation, effort, stamina, and coordination. The physical subscale can range from 0 to 36. It is calculated by adding items 4+6+7+10+13+14+17+20+21.

Cognitive functioning (10 items) concerns concentration, memory, thinking and organization

of thoughts. The cognitive subscale can range from 0 to 40. It is calculated by adding items 1+2+3+5+11+12+15+16+18+19.

Psychosocial functioning (2 items) describes the impact of fatigue upon isolation, emotions, workload, and coping. The psychosocial subscale can range from 0 to 8. It is calculated by adding items 8+9.

All items are scaled so that a higher score indicates a greater level of fatigue. See [Appendix 2](#).

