8.2. GENERAL METHODS

Continuous variables will be summarized using the number of non-missing observations (n), mean, SD, median, minimum, and maximum. Categorical variables will be summarized using counts and percentages.

Unless otherwise specified, the estimated mean and median for a set of values should be displayed to 1 more decimal place than the original values, and SD should be displayed to 2 more decimal places than the original values. The minimum and maximum should be displayed to the same number of decimal places as the original values. Deviations from this convention may arise to take account of the relevance of the precision (e.g., the distance walked in the 12MWT is reported to the nearest cm, but there is no relevance in presenting the mean to the nearest mm). These deviations from convention will be documented in the relevant analysis sections below.

Percentages will be displayed with 1 decimal place; except percentages will not be presented when the count is zero and 100% will be presented as an integer. Unless stated otherwise, percentages of subjects will be based on the number of subjects with non-missing data in the analysis set used for the presentation.

Unless stated otherwise, an on-treatment measurement will be any measurement collected (including scheduled and unscheduled visits) up to the date of last dose plus one day. Drug interruptions will not be considered, i.e., data will not be excluded during a drug interruption if the subject resumes study treatment; this includes the follow-up period for subjects who enrol in REN001-202 at the REN001-201 FU.

In by-visit summary tables, the baseline will be summarized using all available data, but also for each visit using only the baseline data from subjects with available data at the visit; hence the mean change from baseline will equal the mean observed visit value – mean baseline value.

Throughout this document ‘change from baseline’ refers to the actual change from baseline (i.e., observed visit value – baseline value). The baseline definitions are detailed in [Section 8.6](#).

There will be 3 approaches to summarising the data and, unless stated otherwise, all presentations will be presented for each approach. [Figure 1](#) in [Section 2](#) shows the different pathway options a subject can enter REN001-202 and the 5 distinct reporting groups these

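### Mean MFIS percent change from baseline is undefined at a baseline of 0 and usually drifts towards worsening when there is no net group change; drop it and rely on the absolute change already planned

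*SAP*

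**What the plan says.** SAP 4.5 defines the score: "There are 21 items, each of which is scored 0 (never) to 4 (almost always), providing a continuous scale of 0–84". The physical subscale runs 0-36 and the cognitive 0-40; for the shortest, Protocol 7.3.1 says "The psychosocial subscale can range from 0 to 8". On direction, SAP 4.5 says "All items are scaled so that a higher score indicates a greater impact of fatigue", so a positive change reads as worse.

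SAP 4.5 then asks that "changes from baseline and percent changes from baseline will be calculated for each of the sub-scale scores and the total score". SAP 10.2 carries this into the outputs: "Observed, change from baseline and percent change from baseline values will be summarized by visit using descriptive statistics", for the subscales and the total. It adds "The associated 95% confidence intervals for the observed, change from baseline and percent change from baseline means will also be presented", and then "Mean plots of observed, change from baseline and percent change from baseline values, with 95% confidence intervals will be presented by group".

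The following also bear on the point:
- No rule for a zero baseline appears in SAP 4.5, 8.3.1, 8.6 or 10.2. SAP 10.2 allows for subjects at the ends of the scale only in the shift table.
- No entry criterion in Protocol 4.1 to 4.3 sets a minimum MFIS score.
- The endpoint in Protocol 3.2.2 and 3.2.4, repeated in SAP 3.2.2 and 3.2.4, is the absolute value and the change from baseline. Percent change appears only in the SAP's derivation and analysis sections.
- In SAP section 4, the other questionnaires scored against baseline (PROMIS, PGIS, SF-36, BPI, WPAI and the phenotypic questions) use absolute change only. Among the efficacy measures, percent change is otherwise planned only for walk distance.

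**The concern.** Percent change divides by the subject's own baseline, and here that baseline may be 0 or close to it. This has three consequences.

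1. A subject with baseline 0 has no percent change. Such a subject can only stay the same or worsen, so the omission is not neutral. SAP 8.2 restricts the baseline at each visit to subjects with data at that visit, so that mean change equals mean visit value minus mean baseline. The percent rows would rest on a different set of subjects and cannot meet that identity.
2. Improvement stops at -100%, while worsening from a low baseline has a far higher ceiling. The mean is therefore pulled upwards by ordinary fluctuation, and a few low-baseline subjects can dominate it and its interval.
3. The amount of pull depends on where a group's baselines lie. The plan shows groups whose baselines may differ: mtDNA and nDNA subjects, and subjects coming from placebo and from active treatment. Their percent-change curves could separate for that reason alone.

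At stake is how a reader interprets the MFIS percent tables and plots. With no formal testing planned, these displays are all the reader has to go on for that quantity.

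**Working it through.** The documents give no MFIS mean, SD or reliability, and no figure to reproduce. The score ranges come from SAP 4.5; every distributional input below is an assumption.

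**Arithmetic.** Percent change = 100 x (visit - baseline) / baseline.

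| Two subjects swap scores | Mean change | Percent changes | Mean percent change |
|---|---|---|---|
| 1 and 2 | 0 | +100, -50 | +25% |
| 1 and 8 (psychosocial) | 0 | +700, -87.5 | +306% |
| 30 and 40 (total) | 0 | +33.3, -25 | +4.2% |

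- From a baseline of 1 the ceiling is 100 x (max - 1) / 1: +700% psychosocial, +3500% physical, +3900% cognitive, +8300% total. The lower limit is always -100%.
- One psychosocial subject going from 1 to 8 adds 700/50 = 14 points to the mean percent change at n = 50, and 700/150 = 4.7 points at n = 150. The same subject adds 7/50 = 0.14 and 7/150 = 0.05 points to the mean absolute change.
- If every subject's score is unchanged, every percent change with a non-zero baseline is exactly 0. The effect needs within-subject variation.

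**Simulation with no net change.** Each subject has a stable true score and two readings around it, rounded and cut off at the ends of the scale; zero baselines are dropped from the percent change. There are 400,000 subjects per setting. Assumed: baseline mean 35%, 50% or 60% of the range; SD 15% or 22%; test-retest correlation (ICC) 0.7 or 0.9.

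| Score | Mean percent change, lowest to highest setting |
|---|---|
| Total | +0.8% to +24.8% |
| Physical | +0.8% to +18.7% |
| Cognitive | +0.8% to +19.1% |
| Psychosocial | +1.3% to +7.7% |

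- The top figure is the total score at mean 35%, SD 22%, ICC 0.7. There 5.9% of baselines are 0, and the mean absolute change in the remaining subjects is -0.47 points: the percent and absolute summaries of the same people have opposite signs.
- At mean 60%, with the same SD and ICC, the total-score figure is +8.3%. Two groups with no net change would then differ by 24.8 - 8.3 = 16.5 percentage points through baseline level alone.
- Over all subjects the mean absolute change is within 0.04 points of 0 in every setting. The median percent change is 0 in all settings but one, where it is -2.0%.
- 100 x mean change / mean baseline, on all subjects with both readings, stays within 0.1% of 0.

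**Wider and less favourable assumptions.** With means of 30-65%, SD 20-25% and correlation 0.70-0.85, the mean percent change runs from +2.4% to +32% for the total and from +2.4% to +8.7% for psychosocial. At mean 50% and SD 25%, the 95% interval for the mean percent change lies wholly above 0 in about 6-10% of simulated trials at n = 50 and 21-45% at n = 150, for the total and psychosocial scores; the nominal rate is 2.5%.

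**Counter-case.** In a floor-heavy psychosocial setting, with 42% of baselines at 0 and dropped, the mean percent change was -10%, which reads as improvement.

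**The case against.** The strongest reply is that little rests on these outputs. SAP 8.1 plans no testing, and SAP 2 warns that the efficacy data are to be read descriptively. For nDNA subjects MFIS is only exploratory. SAP 8.2 prints "number of non-missing observations (n), mean, SD, median, minimum, and maximum", so dropped zero baselines would show as a smaller n, and a median near 0 beside a positive mean would reveal the skew. Absolute changes with intervals, spaghetti plots and 4-point shift tables are all planned. A single sentence on zero baselines would close the formal gap. The sizes also rest on assumptions: at a mean of 50-60% and SD of 15% the total-score shift is only +0.8% to +4.3%. The share of zero totals depends on the assumed shape: at mean 35% and SD 22%, beta-distributed scores give 0.4% rather than about 6%, although the shift in that corner stays at +9% to +30%.

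Most of this stands, and it limits the point. It does not remove it. A zero-baseline rule settles who is counted but leaves the skew. The mean plots show the mean and its interval without the median that would warn the reader.

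Three stronger readings are tempting, and the documents support none of them:
- A reader might infer that the MFIS results in general would show worsening when no score has moved. Unchanged scores give 0%, and only the percent-change means, intervals and plots are affected.
- A reader might infer that a secondary endpoint is compromised. The endpoint is the absolute value and change, which are sound in this respect.
- A reader might infer a fixed bias against the drug. Size and direction depend on an unknown baseline distribution, and the counter-case reverses.

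**Conclusion.** The concern holds in a limited form. As written, the SAP orders a summary that has no value for some valid baselines, uses a different set of subjects from the absolute change beside it, and usually leans towards worsening when a group has no net change but its members fluctuate. The lean is about +1% to +25% under the assumed baseline means of 35-60% of range, SD of 15-22% of range and ICC of 0.7-0.9. It is a few percent or less where baseline fatigue is high and its spread is modest, and it can change sign if many zero baselines are dropped. The undefined value and the asymmetry follow from the score ranges alone; the sizes do not, and should be quoted only with their assumptions.

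The primary safety objective, the MFIS endpoint as defined, the medians and the shift tables are untouched. The change is worth making because it costs almost nothing and removes a display that can contradict the row next to it.

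**What to change.** Remove percent change from baseline for the three MFIS subscales and the total from SAP 4.5, and from the tables, confidence intervals and mean plots in SAP 10.2. Rely on the observed values, absolute changes and 4-point shift tables already planned.

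If a relative figure is wanted, print 100 x mean change / mean baseline for the group at each visit, on exactly the subjects in the absolute-change row, zero baselines included.

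The cost is a wording change in two SAP sections and fewer outputs. No new data are needed and no protocol endpoint is lost. The downside is the loss of one familiar descriptive display.
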